5.3 LIFESTYLE CONSIDERATIONS

Not applicable.

5.4 SCREEN FAILURES

Screen failures are defined as participants who consent to participate in the clinical study but are not subsequently randomized. A minimal set of screen failure information is required to ensure transparent reporting of screen failure participants to meet the Consolidated Standards of Reporting Trials (CONSORT) publishing requirements and to respond to queries from regulatory authorities. Minimal information includes demography, screen failure reasons, eligibility criteria, and any SAE.

Individuals who do not meet the criteria for participation in this study (screen failure) may be rescreened during the open screening period, provided they meet at that time all inclusion and none of the exclusion criteria. A different participant identification number will be issued, while the other identification for this participant should be recorded as a screen failure. There is no requirement for a waiting period between a screen failure date and the rescreening date.

Screen failure participants can be re-screened, and all screening procedures will have to be re-started for these participants. There is no limitation in the number of times a participant will be screened.

All screening procedures must be repeated except for radiological disease assessment if it has been done in the 28 days prior to novel randomization.

In case the participant is a temporary screen failure, there is no need to have the participant reconsent (ie, sign a new ICF) if the participant ends up participating in the study. However, if the reason for temporary screen failure is a reason that might have altered the initial agreement given by the participant to participate in the study, the Investigator should ensure the willingness of the participant to continue or repeat some screening procedures and to confirm his/her participation in the trial. This oral agreement should be documented in the participant's chart. All tests outside of the protocol window should be repeated and entered to the additional pages.

5.5 CRITERIA FOR TEMPORARILY DELAYING ENROLLMENT/RANDOMIZATION/ADMINISTRATION OF STUDY INTERVENTION

During a regional or national emergency declared by a governmental agency, if the site is unable to adequately follow protocol mandated procedures, contingency measures are proposed in [Section 10.9](#) (Appendix 9: Contingency measures for a regional or national emergency that is declared by a governmental agency) should be considered for screening/enrollment/randomization/administration of study intervention.

6 STUDY INTERVENTION(S) AND CONCOMITANT THERAPY

Study interventions are all pre-specified IMPs, AxMPs, and medical devices and other interventions (eg, surgical and behavioral) intended to be administered to the study participants during the study conduct.

6.1 STUDY INTERVENTION(S) ADMINISTERED

6.1.1 Investigational medicinal products

6.1.1.1 Isatuximab

6.1.1.1.1 Isatuximab IV formulation

Isatuximab will be administered at the dose of 10 mg/kg weekly for 4 weeks (Cycle 1) and Day 1 and 15 of subsequent cycles. The calculation of the Isatuximab IV dose will be based on the most recent weight available.

Isatuximab infusion rate are described in [Table 8](#).

Table 8 - Isatuximab intravenous infusion rate

	Dilution volume	Initial rate	Absence of infusion-related reaction	Rate increment	Maximum rate
First infusion	250 mL	25 mL/hour	60 min	25 mL/hour every 30 minutes	150 mL/hour
Second infusion	250 mL	50 mL/hour	30 min ^a	50 mL/hour for 30 minutes then increase to 100 mL/hour	200 mL/hour
Third and subsequent infusion	250 mL	200 mL/hour			200 mL/hour

^a Applicable to Grade ≥ 2 infusion reactions.

Regarding potential reduction of infusion rates due to IRs active comparator arm, the following steps are recommended:

- **First infusion:** in case of Grade 2 IR during first infusion, infusion could be restarted at one-half (12.5 mL/hour) of the initial infusion rate when the IR improves to Grade ≤ 1 . If symptoms do not recur after 30 minutes, the infusion rate may be increased by 25 mL/hour increments every 30 minutes, up to a maximum of 150 mL/hour, until the total volume is infused.
- **Second infusion:** in case of Grade 2 IR during second infusion, infusion could be restarted at one-half (25 mL/hour) of the initial infusion rate when the IR improves to Grade ≤ 1 . If symptoms do not recur after 30 minutes, the infusion rate may be increased by 50 mL/hour increments every 30 minutes, up to a maximum of 200 mL/hour, until the total volume is infused.

- **Third and subsequent infusions:** in case of Grade 2 IR during third infusion, infusion could be restarted at one-half (100 mL/hour) of the infusion rate when the IR improves to Grade ≤ 1 . If symptoms do not recur after 30 minutes, the infusion rate may be increased by 50 mL/hour increments every 30 minutes, up to a maximum of 200 mL/hour, until the total volume is infused.

Please refer to the pharmacy manual for further details with regards to formulation.

6.1.1.1.2 *Isatuximab SC formulation*

Isatuximab will be administered weekly for 4 weeks (Cycle 1) and on Day 1 and Day 15 of each subsequent cycle, at the nominal dose of 1400 mg.

Isatuximab will be administered by an HCP (either on-site or, from Cycle 6, at-home for D-15, see [Section 4.2](#)) in the periumbilical region at a single site, using an investigational device injector; injection site will be rotated from one administration to the other.

See [Table 9](#) for more detailed description of dose and method of administration.

6.1.1.2 *Dexamethasone*

Dexamethasone will be taken orally at a dose of 40 mg (or 20 mg for participant ≥ 75 years) on Day 1, 8, 15, and 22 (to be repeated every 28 days).

If a dose of dexamethasone is missed, it should be taken as soon as possible within the next 2 days. The dose per cycle must not exceed 160 mg (80 mg if the participant is ≥ 75 years old). Participants will be asked to maintain a diary to record the doses of dexamethasone taken orally (except those administered by the study nurse/ Investigator).

When administered on the same day as other investigational medicinal products (IMP)s, dexamethasone will be administered before all other IMPs.

Particular care is needed when treating participants with glaucoma (or family history of glaucoma) as well as when treating participants with ocular herpes simplex, because of possible corneal perforation, as prolonged use of corticosteroids may produce subcapsular cataracts and glaucoma, and may result in impaired vision including loss of vision. Investigators are recommended to refer to product SmPC of dexamethasone.

6.1.1.3 *Pomalidomide*

Pomalidomide will be taken orally at a dose of 4 mg on Days 1 to 21 (to be repeated every 28 days). Pomalidomide may be taken with water and should be swallowed whole. Participants are not permitted to break, chew, or open the capsules. Pomalidomide should be taken with or without food, preferably at the same time every day. Participants will be asked to maintain a diary to record the doses of pomalidomide (except those administered by the study nurse/Investigator). If a dose of pomalidomide is missed, it should be taken as soon as possible on the same day. If it is missed for the entire day, the dose should not be made up and will be considered omitted (and will not be replaced). The next scheduled dose should be taken at the next scheduled time point.

Participants should be monitored for any new or worsening neurologic, cognitive or behavioral signs and symptoms.

If progressive multifocal leukoencephalopathy (PML) is suspected, study treatments should be put on hold immediately until a diagnosis of PML has been definitively excluded. If suspected, the Investigator should refer participant to a specialist and appropriate diagnosis testing should be initiated [Serial Magnetic resonance imaging (MRI) with contrast and cerebrospinal fluid analysis for John Cunningham Virus] [Please refer to PML diagnostic criteria by American Association of Neurology (AAN) (27)].

If PML is confirmed, pomalidomide should be discontinued and isatuximab and dexamethasone should be put on hold. [Please refer to PML diagnostic criteria by AAN (27)] Isatuximab and dexamethasone could be resumed after recovery of PML based on Investigator's judgement and after discussion with the Sponsor.

Table 9 - Study intervention(s) administered

Intervention label	Isatuximab IV	Isatuximab SC	Dexamethasone	Pomalidomide
Intervention name	Isatuximab IV	Isatuximab SC	Dexamethasone	Pomalidomide
Intervention description	Single use vial	Single use vial	Tablets	Capsules
Type	Drug	Drug	Drug	Drug
Dose formulation	Concentrate solution for IV infusion	Solution for Subcutaneous administration	Tablets	Hard capsules
Unit dose strength(s)	Concentration: 20 mg/mL Dosage presentation: 500 mg/25 mL or 100 mg/5 mL	140 mg/mL isatuximab,	4 mg 8 mg	1 mg 2 mg 3 mg 4 mg
Dosage level(s)	10 mg/kg QW (Cycle 1) 10 mg/kg Q2W (subsequent cycles)	1400 mg QW (Cycle 1) 1400 mg Q2W (subsequent cycles)	40 mg QW for participants <75 years of age 20 mg QW ≥75 years of age	4 mg on Day 1 to 21 in a 28-days cycle
Route of administration	IV	SC	Oral	Oral
Use	Active comparator	experimental	Active comparator	Active comparator
IMP	IMP	IMP	IMP	IMP
Packaging and labeling	Isatuximab (SAR650984) will be provided in 1 glass vial per box. The content of the labeling will be in accordance with the local regulatory specifications and requirements	Study Intervention will be provided in one glass vial per box. Each vial and box will be labeled as required per country requirement	Supplied as blisters containing 10 tablets each (1kit = 2 blisters of 10 tablets into a wallet) except for US where it is supplied in a child resistant bottle containing 100 tablets each	Supplied as blisters of 7 hard capsules each (1 kit = 3 blisters of 7 hard capsules into a wallet).
[Current/former name(s) or alias(es)]	Isatuximab, SAR650984	Isatuximab, SAR650984	Dexamethasone	Pomalidomide

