Grade 1: mild transient reaction; infusion interruption not indicated; intervention not indicated.	Continuation of isatuximab infusion is per the judgment of the Investigator following close direct monitoring of the participant's clinical status. Isatuximab infusion may be stopped at any time if deemed necessary. If stopped, IR will be classified as Grade 2 as per NCI-CTCAE definition.
Grade 2: moderate reaction; therapy or infusion interruption indicated but responds promptly to symptomatic treatment (eg, antihistamines, NSAIDS, narcotics, IV fluids); prophylactic medications indicated for ≤24 hours.	Stop isatuximab infusion. Give additional medication with IV diphenhydramine 25 mg IV (or equivalent) and/or IV methylprednisolone 100 mg (or equivalent) as needed. Isatuximab may be resumed only after participant recovery, at half the infusion rate before the interruption, and with close monitoring, and may be increased subsequently, at the Investigator's discretion.
Grade 3 / 4: severe or life-threatening reaction; Grade 3: Prolonged (eg, not rapidly responsive to symptomatic medication and/or brief interruption of infusion); recurrence of symptoms following initial improvement; hospitalization indicated for clinical sequelae. Grade 4: Life-threatening consequences; urgent intervention indicated.	Stop isatuximab infusion. Give additional medication with diphenhydramine 25 mg IV (or equivalent) and/or IV methylprednisolone 100 mg (or equivalent) and/or epinephrine as needed until the resolution of the AE or until the AE improves to Grade 1. Only then, if previous Grade 3, the infusion may be restarted at the Investigator's discretion; if so, the infusion rate should be half of the initial infusion rate and it may be increased subsequently, at the Investigator's discretion. If the severity of an infusion-related AE returns to Grade 3 after the restart of the infusion, the same procedure described above may be repeated at the Investigator's discretion. If a Grade 3 infusion-related AE occurs for a 3rd time, treatment with isatuximab will be definitely discontinued for that patient. In case of Grade 4, isatuximab will be permanently discontinued.

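### For a Grade 2 infusion reaction in the IV arm, Section 6.1.1.1.1 and Table 16 give different restart rates on the first two infusions whenever the rate has risen above its starting value

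*Protocol*

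**What the plan says.** Two places in the current protocol text cover a Grade 2 infusion reaction in the IV arm.

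**Section 6.1.1.1.1**, below Table 8, goes infusion by infusion:
- First: "infusion could be restarted at one-half (12.5 mL/hour) of the initial infusion rate".
- Second: "infusion could be restarted at one-half (25 mL/hour) of the initial infusion rate".
- Third and later: "infusion could be restarted at one-half (100 mL/hour) of the infusion rate".

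In each case the reaction must first have improved to Grade 1 or less. After 30 minutes without recurrence the rate may go up in fixed steps: 25 mL/hour on the first infusion ("up to a maximum of 150 mL/hour, until the total volume is infused") and 50 mL/hour on later ones ("up to a maximum of 200 mL/hour, until the total volume is infused").

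**Table 16, Grade 2 row (Section 6.5.5)** gives one rule for every infusion: "Isatuximab may be resumed only after participant recovery, at half the infusion rate before the interruption, and with close monitoring". Later increases are left to the Investigator.

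Table 16 refers to half of the initial rate only in its Grade 3/4 row, for a restart after Grade 3. Neither place cites the other or says which prevails.

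**The concern.** The two rules share an event, a grade and an arm, but start from different reference rates. Table 8 raises the rate in steps during the first and second infusions, so the initial rate and the rate before interruption soon separate. A site that follows one passage then departs from the other.

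The rule applies when a participant has just reacted. The protocol's risk assessment (Table 5) says that reactions to IV isatuximab are most common at the first administration, which is where the two rules can lie furthest apart. Different sites could manage the same event differently and each point to the protocol.

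This is an internal contradiction in the text, not a questionable choice of design.

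**Working it through.** **Inputs.** Table 8 gives the initial rates (25, 50 and 200 mL/hour for the first, second and third-plus infusions), the maximum rates (150, 200 and 200 mL/hour), the 250 mL volume, and the first-infusion increment of "25 mL/hour every 30 minutes" after an initial 60 minutes. The two restart rules are those set out above.

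**The plan's own figures.** Section 6.1.1.1.1 rate = initial rate / 2: 25/2 = 12.5; 50/2 = 25; 200/2 = 100 mL/hour. All three reproduce.

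**Comparison.** Table 16 rate = rate before interruption / 2. Ratio = Table 16 rate / Section 6.1.1.1.1 rate.

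First infusion, stepping through Table 8:

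| Rate at reaction (mL/hour) | Step starts at minute | Volume already given (mL) | Table 16 restart | Section 6.1.1.1.1 restart | Ratio |
|---|---|---|---|---|---|
| 25 | 0 | 0 | 12.5 | 12.5 | 1 |
| 50 | 60 | 25 | 25 | 12.5 | 2 |
| 75 | 90 | 50 | 37.5 | 12.5 | 3 |
| 100 | 120 | 87.5 | 50 | 12.5 | 4 |
| 125 | 150 | 137.5 | 62.5 | 12.5 | 5 |
| 150 | 180 | 200 | 75 | 12.5 | 6 |

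The top step is reachable: 50 mL remain at minute 180, and 50/150 × 60 = 20 minutes, so the infusion ends at minute 200.

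Second infusion. The increment cell of Table 8 can be read as steps of 50 throughout, or as one step of 50 followed by a step of 100. Both readings reach 200 mL/hour before the bag is empty (minute 90 with 150 mL given, or minute 60 with 75 mL given).
- Reaction at 50: 25 against 25, ratio 1.
- Reaction at 100: 50 against 25, ratio 2.
- Reaction at 150 (first reading only): 75 against 25, ratio 3.
- Reaction at 200: 100 against 25, ratio 4.

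Third and later infusions at 200 mL/hour: 100 against 100, ratio 1.

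**Other differences, side by side.**

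| | Section 6.1.1.1.1 | Table 16, Grade 2 |
|---|---|---|
| Condition for restart | Reaction improved to Grade 1 or less | Participant has recovered |
| Raising the rate again | Fixed increments after 30 symptom-free minutes | Investigator's discretion |

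These two differences do not depend on the rate, so they remain on the third and later infusions.

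**The case against.** **The wording is permissive.** Section 6.1.1.1.1 recommends and Table 16 offers guidelines; in both, restarting is optional. That stands, but each passage attaches a specific rate to a restart, and the rates differ.

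**Table 16 might mean the initial rate loosely.** It does not read that way. Its Grade 3/4 row names half of the initial rate separately, so the table distinguishes the two bases.

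**Other text might settle it.** Section 6.5 asks for the most conservative adjustment when recommendations conflict, but for a participant with several toxicities and in terms of dose reduction, omission or delay. It does not address two infusion rates for one reaction. Section 4.1 points to Table 8 for the infusion rate, while Sections 6.5 and 6.5.5 point to Table 16 for managing reactions, so the pointers lead to both rules.

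**Six-fold is an extreme.** It is. It needs a reaction in the last 20 minutes of an uninterrupted first infusion, with at most 50 mL left. Re-escalation also narrows the practical gap. With 50 mL left, Section 6.1.1.1.1 gives 30 minutes at 12.5 (6.25 mL), 30 minutes at 37.5 (18.75 mL), then 25 mL at 62.5 (24 minutes), 84 minutes in all. A constant 75 mL/hour takes 40 minutes, so the remaining time differs about two-fold.

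**Stronger readings that the protocol does not support.**
- A reader might infer that the conflict threatens the alpha-controlled key secondary endpoint, incidence of infusion reactions. That endpoint is compared by Fisher's exact test on the safety population (Section 9.2.3.1), and adverse events are summarised by participants with at least one event (Section 9.2.6.1). The restart rule acts only after a Grade 2 reaction, when the participant already counts, and the endpoint is not restricted by grade. A recurrence does not change the count.
- A reader might also infer frequent use from the 38.2% quoted for the earlier Phase 3 trial of IV isatuximab (Section 2.2.3.1). That figure covers all grades; only the Grade 3 to 4 part (2.6%) is split out. The Phase 1b study (Section 2.2.3.2) reports a single Grade 2 reaction among 12 IV participants (1/12 = 8.3%). Neither source says how many reactions began above the initial rate, which is the condition for the rates to conflict.

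**Conclusion.** The contradiction holds on current text. On the first infusion the restart rates differ by a factor of 2 to 6 once the rate has left 25 mL/hour; on the second by up to 4 once it has left 50 mL/hour. They agree at the initial rate, and on third and later infusions running at 200 mL/hour. The differences in restart condition and re-escalation apply to all infusions.

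These factors assume that Table 8 is followed up to the reaction and that it is the first interruption of that infusion. They compare restart rates, not total infusion times.

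The consequence is confined to participant safety and uniform conduct between sites after a reaction. Recurrence at Grade 3 or above would be an event of special interest (Section 8.6.6), and a third Grade 3 event ends isatuximab (Table 16), so the rule could bear on those outcomes; the protocol gives no figure for how much. No effect on a primary or key secondary analysis is shown, and the number of participants affected cannot be derived because the Grade 2 frequency in the larger trial is not given. It is a correction that should be made, with no bearing on the trial's statistical conclusions.

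**What to change.** Reconcile Section 6.1.1.1.1 with the Grade 2 row of Table 16 so that the rule for restarting an IV infusion after a Grade 2 reaction is stated once and cross-referenced from the other place. The single statement should settle three things: the reference rate, the condition for restarting, and how the rate may be raised afterwards. Which rule applies is for the clinical team to decide; this review takes no position.

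The cost is one wording correction in an amendment and a notice to sites. Sample size, endpoints and analyses are unaffected.

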6.1.1.4 Study arms

Table 10 - Study arm(s)

Arm title	Arm SC.	Arm IV.
Arm type	Experimental.	Active comparator.
Arm description	Participants will receive isatuximab SC 1400 mg QW (ie, on Day 1, 8, 15, and 22) in first cycle (28 days) then 1400 mg Q2W (ie, on Day 1 and Day 15) for subsequent 28-day cycles.	Participants will receive isatuximab IV 10 mg/kg QW (ie, on Day 1, 8, 15, and 22) in first cycle (28 days) and then 10 mg/kg Q2W (ie, on Day 1 and Day 15) for subsequent 28-day cycles.
Associated intervention labels	Isatuximab SC. Dexamethasone. Pomalidomide.	Isatuximab IV. Dexamethasone.. Pomalidomide

Abbreviations: IV = intravenous; QW = once a week; Q2W =once every 2 weeks; SC = subcutaneous.

6.1.2 Auxillary medicinal products

All participants will receive premedication to prevent or reduce the incidence or severity of isatuximab-related IRs, at least 15 to 30 minutes (but no longer than 60 minutes) prior to isatuximab infusion (regardless of route). Participants who do not experience IRs after 4 consecutive administrations of isatuximab may have their need for subsequent premedication reconsidered at the Investigator's discretion, except for montelukast which should be administered only on Cycle 1.

The standard premedication regimen will include, in this order:

- Montelukast (ATC code: R03DC03)10 mg PO (or equivalent; to be administered during Cycle 1 only).
- Dexamethasone (ATC code: H02AB02) PO will also be given in the same dose as stated in [Section 6.1.1](#).
 - Methylprednisolone (ATC code: H02AB04) (or equivalent):100 mg IV if dexamethasone is discontinued earlier than isatuximab and premedication is still needed.
- Acetaminophen (paracetamol ATC code: N02BE01) 650 to 1000 mg orally.
- Diphenhydramine (ATC code: R06AA02) 50 mg PO (or equivalent: eg, cetirizine, promethazine, dexchlorpheniramine, according to the approval availability) or Diphenhydramine 25 to 50 mg IV (or equivalent). Intravenous route is preferred for at least the first 4 IV isatuximab infusions.

6.1.3 Devices

Dispensing devices have to be used for administration of isatuximab in the SC arm only.

Preparation and SC administration of isatuximab in the periumbilical region using the (investigational) isatuximab injector device will be performed by study staff. The (investigational) isatuximab injector device is a sterile, single-use, disposable, elastomeric, user-filled wearable injector. The device will be supplied in a blister package into a box. Both the blister package and the box will be labeled according to the local requirements.

The (investigational) isatuximab injector device includes an adhesive backing to secure it to the injection site during administration. Injection sites with the device are permitted only on the abdominal region. At the end of dosing, the injection needle retracts into the device housing and the device enters a locked-out state to prevent reuse.

The volume to be injected at each administration will be injected at a single site; injection site will be rotated from one administration to the next. The administration times including any pauses or stoppages will be recorded for all cohorts.

Further detailed instructions for preparation and administration using the (investigational) isatuximab injector device are provided in Pharmacy Manual. Study staff must be trained on proper use of the device prior to use.

All medical device incidents, including those resulting from malfunctions of the device, must be detected, documented, and reported by the Investigator throughout the study (see [Section 10.7.4](#)).

